The Amplatzer™ Muscular VSD Occluder was approved by the US Food and Drug Administration (FDA) on September 7, 2007. This study is designed to further evaluate the safety and effectiveness in subjects implanted with the Amplatzer Muscular VSD Occluder.

B. Device Description

The Amplatzer Muscular VSD Occluder is a self-expandable, double disc device made from a Nitinol wire mesh. The two discs are linked together by a short connecting waist corresponding to the size of the VSD. In order to increase its closing ability, the discs and waist are filled with polyester fabric. The polyester fabric is securely sewn to the device by a polyester thread.

C. Purpose

The purpose of this study is to further evaluate the safety and effectiveness of the Amplatzer Muscular VSD Occluder.

D. Disease to be Treated

The Amplatzer Muscular VSD Occluder is indicated for use in patients with complex ventricular septal defects (VSD) of significant size to warrant closure (large volume left to right shunt, pulmonary hypertension and/or clinical symptoms of congestive heart failure) who are considered to be at high risk for standard transatrial or transarterial surgical closure based on anatomical conditions and/or based on overall medical condition.

High risk anatomical factors for transatrial or transarterial surgical closure include patients:

- Requiring left ventriculotomy or an extensive right ventriculotomy;
- With a failed previous VSD closure;
- With multiple apical and/or anterior muscular VSDs (“Swiss Cheese Septum”); or
- With posterior apical VSDs covered by trabeculae.

E. Study Type

The objectives of this Amplatzer Muscular VSD Occluder Post Approval Study will be evaluated through a prospective, non-randomized, multi-site clinical study design. The primary safety and efficacy endpoints of this study are intended to be evaluated against the corresponding endpoints of the High Risk Cohort of the Muscular VSD Study.

Clinical Investigational Plan**F. Study Objectives****Primary Safety Objective**

The primary safety objective is to evaluate the proportion of subjects experiencing a serious adverse event within 12 months of the procedure. Since the subject selection criteria will be similar to that used in the High Risk Cohort of the Muscular VSD Occluder Study, the proportion found in the post approval study will be compared for non-inferiority against the observed major adverse event rate from the High Risk Cohort.

Serious Adverse Event

A serious adverse event is defined as any untoward medical occurrence that:

- results in death;
- is a life-threatening adverse event;
- requires inpatient hospitalization or prolongation of existing hospital stay;
- results in persistent or significant disability/incapacity;
- results in congenital anomaly/birth defect;
- or results in a medically significant event, including laboratory abnormalities.

Primary Effectiveness Objectives

The effectiveness objective is to evaluate the proportion of subjects who experience technical success, closure success, and acute procedure success. Results for the three effectiveness endpoints will be reported separately and, like the safety endpoint, will be compared for non-inferiority against the corresponding results of the High Risk Cohort of the Muscular VSD Occluder Study.

Technical Success

Technical success is met for implant attempt subjects in whom a device is successfully deployed in the ventricular septal defect.

Acute Procedure Success

Acute procedure success is met for implant attempt subjects who meet shunt closure success (as defined in the next paragraph) at procedure.

Shunt Closure Success

Shunt Closure Success is met for subjects in whom the defect has less than or equal to two millimeters residual shunt. Shunt Closure Success will be evaluated at the post procedure, 30 day, 6-month, 12-month and annual follow-up visits through 5 years. The effectiveness endpoint for Shunt Closure Success will be based on the evaluation of the one year follow-up visit.

Clinical Investigational Plan

G. Eligibility Criteria

A subject is eligible to participate in the study if he/she meets all inclusion criteria and none of the exclusion criteria.

Patients who previously received an Amplatzer Muscular VSD Occluder following device approval on September 7, 2007, may be eligible to enroll in the study. Refer to **Section I, Part H.** for details.

Inclusion Criteria

1. The Amplatzer Muscular VSD Occluder is indicated for use in subjects with complex congenital muscular ventricular septal defects (VSD) of significant size to warrant closure. Subjects must meet at least one of the following:
 - a. Large volume left to right shunt ($Q_p/Q_s > 2:1$),
 - b. Pulmonary hypertension (PA pressure $> 50\%$ systemic),
 - c. Clinical symptoms of congestive heart failure,
 - d. Banding of the pulmonary artery(ies) and in the opinion of the treating investigator closure of the VSD is clinically warranted.
2. Subjects must meet at least one of the following criteria to be considered high risk for standard transatrial or transarterial surgical closure:
 - a. Left ventriculotomy or an extensive right ventriculotomy, defined as: Due to the location of the VSD the surgeon would have difficulty visualizing and/or repairing the defect through a right atriotomy and therefore would require a ventriculotomy.
 - b. Failed previous VSD closure,
 - c. Multiple apical and/or anterior muscular VSDs (“Swiss Cheese Septum”)
 - d. Posterior apical VSDs covered by trabeculae.
 - e. Overall medical condition
3. Subject/legally authorized representative has signed the informed consent
4. Subject/legally authorized representative is willing to complete the follow-up requirements of this study

Exclusion Criteria

1. Subjects with defects less than 4 mm distance from the semilunar (aortic and pulmonary) or atrioventricular valves (mitral and tricuspid)
2. Subjects with severely increased pulmonary vascular resistance above 7 Wood units and a right-to-left shunt and documented irreversible pulmonary vascular disease
3. Subjects with perimembranous (close to the aortic valve) VSD
4. Subjects with post-infarction VSD
5. Subjects who weigh < 5.2 kg
6. Subjects with sepsis (local/generalized)

Clinical Investigational Plan

7. Subjects with active bacterial infections
8. Subjects with contraindications to anti-platelet

If a subject does not meet at least one of the high risk anatomical conditions (inclusion criteria 2.a. – 2.d.) for standard transatrial or transarterial surgical closure and enrollment is based on overall medical condition (inclusion criteria 2.e.), the condition must be documented in progress notes or the medical record as the condition that meets enrollment criteria.

H. Subject Enrollment

Investigational sites will inform the subject/legally authorized representative of the study and invite them to participate. Informed consent/assent (if applicable) will be obtained from the subject/legally authorized representative prior to performing any study-specific testing per the clinical protocol. The person obtaining consent will verbally review the content of the Informed Consent Form/assent (if applicable) with the subject/legally authorized representative, allow adequate time for questions, and will provide the subject/legally authorized representative a copy of the consent form.

Prospective Patient Enrollment

Once the subject/legally authorized representative has read and understands the Informed Consent Form, he/she will indicate his/her willingness to participate in the study by signing the form. The site will document the informed consent process in the medical record. Following completion of the baseline testing, investigators will determine if the subject meets all of the inclusion criteria and none of the exclusion criteria.

A subject is considered enrolled in the study after he/she has provided informed consent, meets all inclusion criteria, meets no exclusion criteria, and the delivery system enters the subject's body in an attempt to implant the Amplatzer Muscular VSD Occluder (Implant Attempt). Investigational sites will keep a screening log to track screen failures. A screen failure is defined as a patient who signs the informed consent form but is not enrolled in the study.

Retrospective Patient Enrollment

In order for a previously implanted patient to be eligible for study participation, the following conditions must be met:

Clinical Investigational Plan

- 1) The participant met the eligibility criteria outlined in **Section I G. Eligibility Criteria, parts 1 and 2**, prior to the implantation of the Muscular VSD Occluder
- 2) The participant/legally authorized representative signs the study informed consent (and assent, if applicable)
- 3) The participant/legally authorized representative and site agree to follow the participant per the assessment schedule and complete all required assessments from the time of consent going forward
- 4) Only patients with the potential to provide a minimum of baseline, procedure, one-year, and five-year visit data, including echocardiographic data, will be considered for retrospective data collection.

All study related data, including safety and effectiveness endpoints, will be collected and reported on the corresponding Case Report Forms for those visits that have already occurred. Identification of adverse events in retrospectively enrolled subjects will adhere to the study's established guidelines and procedures. Future visits will occur per the assessment schedule and all data will be collected per the protocol requirements.

All eligible patients should be considered for retrospective enrollment.

I. Study Procedure and Assessments

Subjects will be required to undergo the tests noted in Table 1 at the indicated time periods.

If the delivery system enters the subject's body in an attempt to place a device but no device is implanted during the initial procedure, the subject will be discontinued from the study after a 30-day adverse event collection period. This subject will be discontinued from the study even if Re-intervention occurs within the 30-day period.

If the subject signs a consent form, but the delivery system does not enter the subject, the subject will be considered a consented screen failure, for which a discontinuation form must be completed.

If a subsequent catheterization procedure is performed to attempt to close a residual shunt or new muscular VSD with an Amplatzer Muscular VSD Occluder, this will be classified as a Re-intervention. Data regarding Re-intervention(s) will be captured on new Baseline/Procedure forms for all subjects who meet Technical Success at the initial implant procedure. All follow-up visits will be calculated based on the initial procedure date.

Clinical Investigational Plan

Table 1: Main Data Requirements

	Pre-Procedure	Procedure	Post procedure (+ one day)	30 days (+/- 7 days)	6 Months (+/- 30 days)	One Year (+ 60 days)	Two Year (+/- 180 days)	Three Year (+/- 180 days)	Four Year (+/- 180 days)	Five Year (+/- 180 days)
Physical Exam	✓		✓	✓	✓	✓	✓	✓	✓	✓
ECG	✓		✓	✓	✓	✓	✓	✓	✓	✓
Echo ¹	✓		✓	✓	✓	✓	✓	✓	✓	✓
Cardiac catheterization		✓								
TEE or ICE		✓								
AE Assessment		✓	✓	✓	✓	✓	✓	✓	✓	✓
Chest X-ray AP and lateral	✓		✓			✓	✓	✓	✓	✓
Fluoroscopy ²						✓	✓	✓	✓	✓

¹ Echocardiographic data at Baseline/Procedure can include TTE, TEE and/or ICE.

Echocardiographic image data must be submitted to the sponsor for one year visits.

² Fluoroscopy required if chest x-rays are read as “uncertain” with regard to wire fracture.

1. Implant Procedure

Reference the Amplatzer Muscular VSD Occluder and Delivery System Instructions for Use (IFU) for implant procedure techniques. The Amplatzer Muscular VSD Occluder is to be implanted percutaneously by catheter technique.

2. Closure Assessment

Assessment of VSD closure will be conducted post device deployment during the procedure, at the post procedure follow-up visit, at the 30-day follow-up visit, at the six month follow-up visit, at the one year follow-up visit and at annual visits until the five year visit is complete. Investigators are required to record echocardiographic data to document closure status and submit the data to the sponsor on case report forms in the remote data entry system. An independent Echocardiography Board or Core Laboratory will review the one-year echocardiograms to verify closure status.

3. Follow-up Compliance Measures

Abbott (ABT) will have a dedicated staff to train and manage sites on the importance of protocol compliance, assist sites with reminders, and compensate sites to help ensure adequate subject follow-up. ABT will send reminders to each site regarding upcoming visits. Each enrolled subject will receive a visit notification card. Whenever possible, the site should schedule the next subject follow-up visit at the time of the current visit. Sites will be compensated for the time it takes for the investigator to complete the case report forms. As part of CRF completion reimbursement, sites will be compensated for time spent notifying and reminding subjects of upcoming follow-up visits. If a site becomes non-compliant, enrollment may be halted until the site initiates the appropriate steps to correct compliance.

Clinical Investigational Plan**4. Device Explant**

If a subject has a device explanted during the study, the timing of the explant determines whether the subject is followed further or discontinued from the study. If the device explant occurs before the 12-month visit and a Serious Adverse Event (SAE) is associated with the device explant, the subject will be discontinued on the date the device is explanted. (In this case, the subject is considered a failure for all endpoints except Technical Success.) If a device explant is not associated with a SAE, the subject will continue to be followed through the 12-month visit. The subject will then be discontinued at the 12-month visit.

If a subject has a device explanted after the 12-month visit, the subject will be discontinued on the date of the explant procedure.

J. Adverse Event Reporting

Safety surveillance and reporting starts as soon as the patient is enrolled in the clinical study. Safety surveillance and reporting will continue until the last follow-up visit has been performed, the subject is deceased, the subject concludes participation in the clinical study or the subject withdraws from the clinical study.

For subjects that do not receive a device

If the delivery system enters the subject's body in an attempt to place a device but no device is implanted, the patient will be followed for reportable adverse events for 30 days. The subject should attend a 30-day (+/- 7 days) visit for an adverse event assessment and then be discontinued.

Adverse event data will be collected throughout the time period defined above and will be reported to the Sponsor on a CRF. Additional information with regard to an adverse event should be updated within the appropriate CRF.

For the purposes of this study, the following event types will be reported:

- All serious adverse events

SAE Reporting

The investigator should report all SAEs to the Sponsor as soon as possible but no later than outlined below. For retrospective subjects, the reporting timeframe does not apply to SAEs that occur prior to the informed consent date.

Clinical Site	Reporting timelines
---------------	---------------------

Clinical Investigational Plan

All Sites	SAEs must be reported to the Sponsor no later than 3 calendar days from the day the site personnel became aware of the event or as per the investigative site's local requirements, if the requirement is more stringent than those outlined above.
-----------	---

The date the site staff became aware the event met the criteria of an SAE must be recorded in the source document. The Investigator will further report the SAE to the local IRB/EC according to the institution's IRB/EC reporting requirements.

K. Study Duration

This study will enroll [REDACTED] Each study subject receiving a device will be followed for 60 months post-procedure, unless the device is explanted (See Section I.5 regarding Device Explant).

Clinical Investigational Plan**II. Statistical Analysis**

Analysis will include prospectively and retrospectively enrolled subjects, unless otherwise specified.

The primary safety objective is to evaluate the proportion of subjects experiencing a serious adverse event within 12 months of the procedure. [REDACTED]

[REDACTED]

[REDACTED]

[REDACTED]

[REDACTED]

Similarly, the three effectiveness objectives are the proportion of subjects who experience technical success, acute procedure success, and shunt closure success. In

[REDACTED]

Note: technical success analysis will include only prospectively enrolled subjects.

[REDACTED]

[REDACTED]

Clinical Investigational Plan

[REDACTED]

[REDACTED]

[REDACTED]

[REDACTED]

[REDACTED]

[REDACTED]

The analysis of technical success and acute procedure success will be conducted on all subjects who have an attempted device placement (defined as the delivery system enters the subject's body in an attempt to place a device). The analysis of shunt closure success will be conducted on the study population who has a 12-month follow-up visit. The serious adverse event endpoint will be evaluated on all subjects who have a 12-month follow-up visit or who had a serious adverse event prior to the 12-month visit. For all analyses, a secondary analysis will be conducted on the entire study population, including subjects that are classified as lost to follow-up. In the situation classified as lost to follow-up, subject's last known (reported) status will be used in the calculations.

[REDACTED]

[REDACTED]

Clinical Investigational Plan**III. Study Management****A. Investigators and Sites**

A list of institutions and investigators will be completed and sent to the FDA or other regulatory authorities upon request and as required by applicable regulations.

B. Monitoring Procedures

Monitoring will be conducted according to the ABT Clinical Monitoring standard operating procedure.

Prior to beginning the study, ABT will contact the investigator or designee to discuss the study and data requirements. An ABT monitor will periodically review the subject records and associated source documents.

The investigator shall make subject and study records available to the clinical monitor for monitoring.

C. Data**1. Source Data and Documentation**

All study findings must be documented as source data. Source data are all information in original records (or certified copies of original records) of clinical findings, observations, or other activities in a clinical study necessary for the reconstruction and evaluation of the study. Source data are contained in source documents (e.g., hospital records, clinical and office charts, laboratory notes, memoranda, evaluation checklists, recorded data from automated instruments, study worksheets, or subject files). The investigator uses source documentation to complete the Case Report Forms (CRF). The investigator is required to verify that he/she has reviewed the recorded data. It will be the responsibility of the Investigator to verify all case report forms and ensure data is submitted to ABT in a timely fashion.

2. Data Collection and Processing

Remote data entry will be used to collect all subject data during the study. The investigator, or an individual designated by him/her, is responsible for completing the appropriate CRFs. ABT will handle data per current standard operating procedures. Edit checks built into the database will help ensure data integrity.

Subject information shall be de-identified prior to sending any source documents to ABT. Data collected during this study will be analyzed by ABT or its contractors and submitted to the FDA.

Clinical Investigational Plan

3. Confidentiality and Protection of Study Files

Hard copy information will be stored in controlled files when not in use. Electronic data protection and confidentiality will be ensured by use of passwords allowing different levels of access to computer files based on necessary access (e.g., read only vs. data entry access).

D. Records and Reports

1. Case Report Forms

The investigator, as well as the support staff, will be instructed on content of the case report forms. Case report forms should be submitted via the remote data entry system as soon as possible after implantation and after the subsequent follow-up visit(s). A record will be created in a database for each subject in the study. Records will be updated as the study progresses.

2. Lost-to-Follow-Up

Thorough documentation for contact attempts must be completed for subjects considered by the investigator/site to be lost-to-follow-up. A minimum of three attempts to contact the subject must be made, with at least one of them via certified/signature required mail to the subject's last known address.

3. Investigator Records

Investigators are responsible for maintaining records as required per applicable laws, regulations, and IRB/EC requirements. Records include the following:

- Correspondence with the FDA, other regulatory authorities, the sponsor, IRB/ EC, and other investigators relating to this investigation.
- Subject records, including informed consent, electronic case report forms, and supporting documents (echo reports, etc.).
- Protocol and documentation of, and reasons for protocol deviations.

4. Investigator Reports

Investigators are responsible for preparing and submitting all records as required per applicable laws, regulations, and IRB/EC requirements.

5. Sponsor Records & Reports

ABT is responsible for maintaining records and completing reports as required per applicable laws, regulations, and ABT standard operating procedures.

6. IRB/EC Records

Each reviewing IRB/EC must maintain records as required per applicable laws, regulations, and IRB/EC requirements.

Clinical Investigational Plan**E. Protocol Adherence****1. Protocol Deviation**

Deviations from the investigational plan may be identified at the site or by in-house ABT personnel, and will be recorded on the Deviation CRF. The site is responsible for notifying their IRB/EC of deviations as applicable.

Examples of deviations from the investigational plan include:

- Required testing not completed or done outside window
- Subject seen outside of protocol-defined window
- SAE not reported
- Protocol-required testing done prior to signing the Informed Consent Form
- Inclusion/exclusion criteria not met
- Required subject follow-up not completed
- Subjects enrolled after expiration or during a lapse of IRB/EC approval
- Depending on IRB/EC requirements, continued follow-up of subjects after expiration of IRB/EC approval (or during a lapse in approval)

Investigator compliance will be continuously assessed by the Clinical Affairs management team and compliance will be secured when applicable.

2. Regulatory Documents

The FDA regulations, as well as ABT policies, require that certifications and other regulatory documents be kept up-to-date at all times during the conduct of a clinical investigation.

3. IRB/EC Approval and Continued Renewal

Written documentation of IRB/EC approval for the protocol and sponsor-approved informed consent including HIPAA authorization for the study must be received by ABT prior to enrollment of subjects. The IRB/EC must review and approve the continuation of the study at a minimum of annually from the initial approval date until the study is officially closed out at a site.

4. Approval to Enroll

Investigators must receive written approval from ABT prior to enrolling study subjects.

F. Review Boards**1. CEC**

An independent Clinical Events Committee (CEC) will be utilized to adjudicate reported adverse events. Members of the CEC will have no affiliation with the Muscular VSD Clinical Study. This committee will be composed of at least three

Clinical Investigational Plan

clinicians with expertise in VSD closure. The CEC will review and adjudicate events reported by investigators as defined in the CEC charter.

2. Echocardiography Board

An independent Echocardiography Board or Core Laboratory will review one year echocardiograms to verify closure status. The Board or Core Laboratory may also evaluate echocardiographic images as necessary for analysis of endpoints.

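### The five-year data condition for retrospective entry appears to bar patients explanted before consent, while a prospective subject explanted before 12 months with an SAE counts as a failure in the same pooled analysis

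*Protocol*

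**What the plan says.** Retrospective entry (Protocol Section I.H, condition 4) is limited as follows: "Only patients with the potential to provide a minimum of baseline, procedure, one-year, and five-year visit data", with echo data among them. Condition 3 adds agreement to all assessments from consent onward. Prospective subjects are enrolled at the implant attempt and face no equivalent of condition 4.

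Protocol Section I.I.4 has three branches for explants:

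- Before the 12-month visit, with an associated SAE: "the subject will be discontinued on the date the device is explanted", and "the subject is considered a failure for all endpoints except Technical Success".
- Without an associated SAE: "If a device explant is not associated with a SAE, the subject will continue to be followed through the 12-month visit", after which the subject is discontinued. No failure rule is attached.
- Later: "If a subject has a device explanted after the 12-month visit, the subject will be discontinued on the date of the explant procedure".

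On pooling, Protocol Section II says: "Analysis will include prospectively and retrospectively enrolled subjects, unless otherwise specified". The one visible exception is "Note: technical success analysis will include only prospectively enrolled subjects".

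Section II also sets the analysis sets. Acute procedure success uses all attempted placements. The SAE endpoint uses subjects with a 12-month visit or an earlier SAE. Shunt closure uses subjects with a 12-month visit.

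**The concern.** Read together, the entry rule and the explant rule treat the same event differently by route. An explant before 12 months with an SAE makes a prospective subject a failure. If it happened before a retrospective patient's consent, that patient seems unable to enter at all, because no five-year visit can follow.

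Retrospective entry would then depend on what happened after implant, and part of what happened is what the primary endpoints measure. Those endpoints are complete at 12 months, so five-year data are not needed to score them.

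Patients who are never entered cannot be recovered by any analysis. They may not even be visible: Section I.H defines a screen failure as someone who signed consent, so a candidate ruled out beforehand need not be logged.

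**Working it through.** **Plan's own figure.** SAP 5.3 needs 80 evaluable subjects and enrols 100. With the 80% follow-up floor in SAP 3.0, 80 / 0.80 = 100, which reproduces. The basis for 80 cannot be checked because the assumed rates and the significance level are redacted.

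**Which explants matter, by endpoint.**

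- *SAE.* A prospective subject with an early SAE-associated explant stays in the set, because an earlier SAE is enough. The asymmetry holds.
- *Acute procedure success.* All attempted subjects are in the set, and I.I.4 scores this subject a failure. The asymmetry holds, provided I.I.4 is applied in the analysis; the SAP's visible definition does not repeat it.
- *Shunt closure.* This subject is discontinued before a 12-month visit. Section II then leaves the subject out, while I.I.4 counts a failure. The asymmetry exists only if I.I.4 prevails.
- *Technical success.* Prospective only, so unaffected.

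**Inputs from the SAP.** n = 80 (5.3); goals 63.2% for SAE (5.1.1.1), 61.3% for acute success (5.1.2.2) and 58.7% for closure (5.1.2.3).

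**Assumptions, not in the documents.** e is the share of otherwise eligible patients with an SAE-associated explant before 12 months, f is the retrospective share, and tests are exact binomial, one-sided 5%. True rates p sit at the goals, so any success is a false one. All such explants are assumed to precede consent in the retrospective group.

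**Formulas.**

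- Retrospective SAE rate = (p − e) / (1 − e)
- Retrospective success rate = p / (1 − e)
- Pooled rate = (1 − f) × p + f × retrospective rate

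**Example, e = 5%, f = 50%.**

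- SAE: (0.632 − 0.05) / 0.95 = 0.6126; pooled 0.5 × 0.632 + 0.5 × 0.6126 = 62.2%.
- Acute: 0.613 / 0.95 = 0.6453; pooled 62.9%.
- Closure, if I.I.4 prevails: 0.587 / 0.95 = 0.6179; pooled 60.2%.

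**Critical values and size without selection.** SAE passes with at most 42 events (size 3.2%), acute with at least 57 successes (4.1%), closure with at least 55 (4.2%).

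| f | e | SAE: pooled rate, risk | Acute: pooled rate, risk | Closure if I.I.4 prevails: pooled rate, risk |
|---|---|---|---|---|
| none | none | 63.2%, 3.2% | 61.3%, 4.1% | 58.7%, 4.2% |
| 25% | 1% | 63.1%, 3.4% | 61.5%, 4.4% | 58.8%, 4.4% |
| 25% | 3% | 62.9%, 3.6% | 61.8%, 5.0% | 59.2%, 5.0% |
| 50% | 5% | 62.2%, 4.8% | 62.9%, 7.5% | 60.2%, 7.3% |
| 50% | 10% | 61.2%, 7.1% | 64.7%, 13.3% | 62.0%, 12.7% |

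At one-sided 2.5% the pattern is the same. With f = 50% and e = 5–10%, SAE risk goes from 1.9% to 2.9–4.5% and acute from 2.4% to 4.6–8.8%. With f = 25% and e = 2%, they reach only 2.1% and 2.8%.

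**The case against.** The strongest reply is that the exclusion is inferred. No criterion names prior explant, 'potential' is not defined, I.I.4 is written for explants during the study, and the protocol asks that all eligible patients be considered. A patient without the device could still attend an echo visit, and one explanted after the five-year visit could supply everything required. This stands as a limit on wording: the patient appears ineligible on the natural reading, and sites could read the condition differently. That is itself a reason to settle it.

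Several stronger conclusions that a reader might draw are not supported:

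- *That closure is biased outright.* Section II, as visible, drops the early SAE-associated explant from the closure set on both routes. The bias depends on which passage governs.
- *That every missing explant hides a failure.* Only the SAE-associated explant before 12 months is an automatic failure. Explants without an SAE carry no such rule, and later ones already have a one-year result that may be a success.
- *That five-year visit data favour the retrospective group.* Prospective subjects explanted before year five are discontinued too, so neither route supplies those visits.
- *That the whole study could be retrospective.* Technical success is a primary endpoint tested in prospective subjects only, so some must be prospective.

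Finally, pooling applies unless otherwise specified, and the SAP analysis populations for SAE, acute success and closure are redacted. Handling by route may exist out of sight. It could reveal a difference between routes, but could not restore patients who were never enrolled.

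**Conclusion.** The point holds in limited form. Followed as written, conditions 3 and 4 with I.I.4 appear to screen out of the retrospective group an event that is scored as failure in the prospective group. The effect on the pooled SAE and acute procedure success results is in the device's favour. For shunt closure it is conditional on an unresolved conflict between Sections I.I.4 and II.

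The documents do not fix the size. It is negligible if early SAE-associated explants are rare and few subjects are retrospective, and material if explants reach 5–10% and half the subjects are retrospective. Nothing in the documents supports a particular explant rate. The figures also rest on the assumed alpha, on true rates at the goals, and on I.I.4 being applied to acute success.

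**What to change.** Amend condition 4 so that the one-year and five-year requirement is met either by the visit data or by documentation that the device was explanted before that visit. State that these patients are scored under I.I.4 exactly as prospective subjects are, and that condition 3 covers only visits still due under I.I.4. Reconcile the I.I.4 failure rule with the 12-month-visit restriction for shunt closure in Section II, and carry the result into the SAP.

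Two inexpensive additions would help even if enrolment is complete: log every retrospective candidate with the reason for non-entry, and report the SAE, acute success and closure results by enrolment route.

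The cost is a small protocol amendment with matching SAP text. Whether consent forms or CRFs need changes cannot be judged from the documents. Success and SAE rates may look slightly less favourable.
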